2.2 Hepatitis

Definition: A disorder characterized by a viral pathologic process involving the liver parenchyma

Diagnostic work-up

Monitor patient for abnormal liver blood tests: AST, ALT, and bilirubin prior to each infusion and/or weekly if G1 liver function test elevations. No treatment is recommended for G1 liver function test abnormality

For G2 or higher:

Work-up for other causes of elevated liver enzymes should be tested, viral hepatitis, alcohol history, iron study, thromboembolic event, liver ultrasound, cross-sectional imaging for potential liver metastasis from primary malignancy. If suspicion for primary autoimmune hepatitis is high, can consider ANAs, antismooth muscle antibodies, antineutrophil cytoplasmic antibodies. If patients with elevated alkaline phosphatase alone, g-glutamyl transferase should be tested. For isolated elevation of transaminases, consider checking CK for other etiologies

Grading	Management
All patients	
Counsel all patients to be aware of and inform their health care provider immediately if they experience: Yellowing of skin or whites of the eyes Severe nausea or vomiting Pain on the right side of the abdomen Drowsiness Dark urine (tea colored) Bleeding or bruising more easily than normal Feeling less hungry than usual

G1: Asymptomatic (AST or ALT > ULN to 3.0 x ULN and/or total bilirubin > ULN to 1.5 x ULN)	
Continue ICPI with close monitoring; consider alternate etiologies Monitor laboratories one to two times weekly

G2: Asymptomatic (AST or ALT > 3.0 to ≤ 5 x ULN and/or total bilirubin > 1.5 to ≤ 3 x ULN)	
Manage with supportive care for symptom control Hold ICPI temporarily and resume if recover to G1 or less on prednisone ≤ 10 mg/d For Grade 2 hepatic toxicity with symptoms, may administer corticosteroid 0.5-1 mg/kg/d prednisone or equivalent if the abnormal elevation persists with significant clinical symptoms in 3-5 days Increase frequency of monitoring to every 3 days Infiximab might not be the most appropriate treatment option in the situation of immune-mediated hepatitis given the potential risk of idiosyncratic liver failure (Note: No clear evidence shows the liver toxicity from infiximab from other studies) In follow-up, may resume ICPI treatment followed by taper only when symptoms improve to G1 or less and corticosteroid ≤ 10 mg/d; taper over at least 1 month Patients should be advised to stop unnecessary medications and any known hepatotoxic drugs

G3: Symptomatic liver dysfunction, fibrosis by biopsy, compensated cirrhosis, reactivation of chronic hepatitis (AST or ALT 5-20 x ULN and/or total bilirubin 3-10x3 ULN)	
Permanently discontinue ICPI Immediately start corticosteroid 1-2 mg/kg methylprednisolone or equivalent If corticosteroid refractory or no improvement after 3 days, consider mycophenolate mofetil or azathioprine (if using azathioprine should test for thiopurine methyltransferase deficiency) Laboratories at daily or every other day; consider inpatient monitoring for patients with AST/ALT > 8 x ULN and/or elevated TB 3 x ULN Increase frequency of monitoring to every 1-2 days

G4: Decompensated liver function (e.g, ascites, coagulopathy, encephalopathy, coma; AST or ALT > 20 x ULN and/or total bilirubin > 10 x ULN)

Infliximab might not be the most appropriate treatment option in the situation of immune-mediated hepatitis given the potential risk of liver failure (Note: No clear evidence shows that the liver toxicity from infliximab from other studies); alternatives include non-TNF- α agents as systemic immunosuppressants. If no improvement is achieved with corticosteroids or for patients on combination therapy with a novel agent, with standard chemotherapy, or with targeted therapy, refer to hepatologist for further pathologic evaluation of hepatitis.

Corticosteroid taper can be attempted around 4-6 weeks; re-escalate if needed; optimal duration unclear.

Permanently discontinue ICPI.

Administer 2 mg/kg/d methylprednisolone equivalents.

If corticosteroid refractory or no improvement after 3 days, consider mycophenolate mofetil.

Monitor laboratories daily; consider inpatient monitoring.

Avoid the use of infliximab in the situation of immune-mediated hepatitis.

Hepatology consult if no improvement was achieved with corticosteroid.

Corticosteroid taper can be attempted around 4-6 weeks when symptoms improve to G1 or less; re-escalate if needed; optimal duration unclear.

Consider transfer to tertiary care facility if necessary.

All recommendations are expert consensus based, with benefits outweighing harms, and strength of recommendations is moderate.

*not approved in Japan.

Abbreviations: ADL, activities of daily living; ALT, alanine aminotransferase; ANA, antinuclear antibody; AST, aspartate aminotransferase; CBC, complete blood count; CK, creatine kinase; CMV, cytomegalovirus; CRP, C-reactive protein; CT, computed tomography; CTCAE, Common Terminology Criteria for Adverse Events; CTLA-4, cytotoxic T-cell lymphocyte-4; EGD, esophagogastroduodenoscopy; ESR, erythrocyte sedimentation rate; G, Grade; GI, gastrointestinal; HIV, human immunodeficiency virus; ICPI, immune checkpoint inhibitor; irAE, immune-related adverse event; IV, intravenous; PD-1; programmed death 1; PD-L1, programmed death-ligand 1; TB, tuberculosis; TNF, tumor necrosis factor; TSH, thyroid-stimulating hormone; ULN, upper limit of normal.

Table A3 Management of Lung irAEs in Patients Treated With ICPis

3.0 Lung Toxicities

3.1 Pneumonitis

Definition: Focal or diffuse inflammation of the lung parenchyma (typically identified on CT imaging)

No symptomatic, pathologic, or radiographic features are pathognomonic for pneumonitis

Diagnostic work-up

Should include the following: CXR, CT, pulse oximetry

For G2 or higher, may include the following infectious work-up: nasal swab, sputum culture and sensitivity, blood culture and sensitivity, urine culture and sensitivity

Grading	Management
G1: Asymptomatic, confined to one lobe of the lung or < 25% of lung parenchyma, clinical or diagnostic observations only	Continue ICPi if clinically indicated. Monitor participants weekly or more frequently as needed with history, physical examination and pulse oximetry; may also offer CXR. May offer one repeat CTscan in 3-4 weeks; in patients who have had baseline testing, may offer a repeat spirometry/DLCO in 3-4 weeks If symptoms appear and/or changes in the physical exam are noted, treat as G2
G2: Symptomatic, involves more than one lobe of the lung or 25%-50% of lung parenchyma, medical intervention indicated, limiting instrumental ADL	Hold ICPi until resolution to G1 or less Prednisone 1-2 mg/kg/d and taper by 5-10 mg/wk over 4-6 weeks Consider bronchoscopy with BAL Consider empirical antibiotics Monitor every 3 days with history and physical examination and pulse oximetry, consider CXR; no clinical improvement after 48-72 hours of prednisone, treat as G3
G3: Severe symptoms, hospitalization required, involves all lung lobes or 50% of lung parenchyma, limiting self-care	Permanently discontinue ICPi Empirical antibiotics; (methyl)prednisolone IV 1-2 mg/kg/d; no improvement after 48 hours, may add infliximab 5 mg/kg or mycophenolate mofetil IV 1 g twice a day or IVIG for 5 days or cyclophosphamide; taper corticosteroids over 4-6 weeks
ADL, oxygen indicated	Pulmonary and infectious disease consults if necessary
G4: Life-threatening respiratory compromise, urgent intervention indicated (intubation)	Bronchoscopy with BAL ± transbronchial biopsy
	Patients should be hospitalized for further management

Additional considerations

GI and Pneumocystis prophylaxis with PPI and Bactrim may be offered to patients on prolonged corticosteroid use (> 12 weeks), according to institutional guidelines

Consider calcium and vitamin D supplementation with prolonged corticosteroid use

The role of prophylactic fluconazole with prolonged corticosteroid use (> 12 weeks) remains unclear, and physicians should proceed according to institutional guidelines

Bronchoscopy + biopsy; if clinical picture is consistent with pneumonitis, no need for biopsy

All recommendations are expert consensus based, with benefits outweighing harms, and strength of recommendations are moderate.

Abbreviations: ADL, activities of daily living; BAL, bronchoalveolar lavage; CT, computed tomography; CXR, chest x-ray; DLCO, diffusing capacity of lung for carbon monoxide; G, Grade; GI, gastrointestinal; ICPi, immune checkpoint inhibitor; irAE, immune-related adverse event; IV, intravenous; IVIG, intravenous immunoglobulin; PPI, proton pump inhibitor.

Table A4 Management of Endocrine irAEs in Patients Treated With ICPis

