4.3 Justification for Dose

The RP2D for M7824 is 1200 mg administered as an intravenous infusion q2w. The selection of RP2D is based on the available clinical data from Phase I Study EMR200647-001 and Study MS200647-0008, including safety/tolerability, pharmacokinetics (PK), and pharmacodynamic (such as PD-L1 target occupancy [TO] in peripheral blood mononuclear cells (PBMC) and TGFβ trapping in blood), as well as efficacy in 2L NSCLC cohorts from Study EMR200647-001. The selection of RP2D is also supported by population PK (pop PK) and exposure-response modeling and simulation.

Safety/tolerability in Phase I

The highest dose for M7824 tested in EMR200647-001 was 30 mg/kg, which corresponds to 2100 mg for a 70-kg participant (the median body weight in the current dataset) and to 2400 mg for an 80-kg participant (corresponding to a typical median body weight for solid tumor type participants) (Freshwater, 2017; Bajaj, 2017; Zhao, 2017). Based on clinical observations, M7824 is well tolerated up to 30 mg/kg and the maximum tolerated dose was not reached. In addition, for the 2 dose levels evaluated in 2L NSCLC cohorts of Study EMR200647-001 (500 and 1200 mg iv q2w), overall safety findings were comparable and consistent with observed safety profile in Studies EMR200647-001 and MS200647-0008.

CCI and Phase I dose escalation PK and CCI

The PK dose-proportionality, peripheral PD-L1 TO/TGFβ trapping from the dose escalation phase of Study EMR200647-001 (at doses of 1, 3, 10, 20, and 30 mg/kg q2w), and CCI

CCI

In participants with

CCI

Flat dose rationale

To achieve less variability in exposure, mitigate the risk of dosing errors, reduce the time necessary for dose preparation, and reduce drug wastage compared with the weight-based dosing, a flat dose approach was adopted for expansion phases of Phase I clinical studies.

The flat dosing approach for Phase II is supported by pop PK modeling and simulation using data from 350 participants from the 2 Phase I clinical studies of M7824 in multiple solid tumor types, which showed that although body weight was found to be a covariate for clearance, the estimated magnitude of the body weight exponent on clearance is < 0.5 , predicting less exposure variability from flat dosing than that from body weight-based dosing (Wang, 2009). Accordingly, simulations of AUC and C_{trough} showed that variability in exposure was indeed slightly lower for flat dosing compared with weight-based dosing.

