6.8.2 Adverse Drug Reactions Requiring Treatment Discontinuation

Adverse drug reactions are defined in this study as any AEs related to study intervention assessed by the Investigator and/or Sponsor. Serious adverse reactions are ADRs which are assessed as serious. Any questions or concerns with regards to management and/or follow-up of ADRs should be discussed with the Medical Monitor.

Immune-related AEs, IRRs including hypersensitivity, anemia, TGF β -mediated skin reactions, and bleeding events are managed and followed-up in their respective sections as indicated below. Permanent Treatment discontinuation may be recommended, so the relevant section must be reviewed:

- For management and guidance of suspected irAEs, see Section 6.9.2.
- For infusion-related reactions and hypersensitivity reactions guidance, see Section 6.9.1.
- For anemia guidance, see Section 6.9.4.
- For guidance and management for potentially TGF β mediated skin AEs, see Section 6.9.3
- For guidance and management of bleeding events, see Section 6.9.5.

General guidance:

- In any case, if ≥ 2 doses are missed due to AE, the Medical Monitor should be consulted.
- Inability to reduce corticosteroid dose to 10 mg or less of prednisone or equivalent per day within 12 weeks is an indication for permanent treatment **discontinuation** (except for use of steroids as hormone substitution).
- Persistent Grade 2 or 3 adverse reactions (excluding endocrinopathies controlled with hormone replacement therapy) that do not recover to Grade ≤ 1 within 12 weeks after last dose of study intervention is an indication for permanent treatment discontinuation.

Grade 4 ADRs:

- Participants with Any Grade 4 ADRs require permanent treatment discontinuation except:
 - a. Isolated laboratory values out of normal range that do not have any clinical correlation. Discuss with Medical Monitor regarding work-up, management, and treatment continuation versus hold versus discontinuation for isolated Grade 4 laboratory abnormalities.
 - b. Endocrinopathies controlled with hormone replacement therapy.
 - c. If alternative explanation is identified for Grade 4 non-tumor bleeding.

See Section 6.9.2 for other suspected Grade 4 irAEs, as most require permanent treatment discontinuation.

Grade 3 ADRs:

1. Participants with any severe or Grade 3 treatment-related adverse reactions that recur should be permanently discontinued. Exceptions may be considered as follows after discussion with Medical Monitor:

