6.9.2 Immune-related Adverse Events

Immune-related AEs are specific to immunotherapies and vary by organ system. Immune-related AEs are considered AESIs for both M7824 and pembrolizumab.

In general, the spectrum of irAEs are similar for both M7824 and pembrolizumab.

The following irAEs are important identified risks for M7824.

- Immune-related pneumonitis
- Immune-related hepatitis
- Immune-related colitis
- Immune-related nephritis and renal dysfunction
- Immune-related endocrinopathies (thyroid disorders, adrenal insufficiency, type 1 diabetes mellitus, pituitary disorders)
- Immune-related rash
- Other immune-related events (myositis, myocarditis, encephalitis)

The following irAEs are important potential risks for M7824:

-
- Guillain-Barré syndrome
 - Uveitis
 - Pancreatitis
 - Myasthenia gravis/myasthenic syndrome

The Medical Monitor may be involved as needed for Follow-up. Details of the diagnostic work-up will be requested by the study team.

The recommendations for irAE management, are guided by the joint American Society of Clinical Oncology (ASCO) Clinical Practice Guidelines (Brahmer, 2018) and National Comprehensive Cancer Network (NCCN) (NCCN Guidelines®), listed in Appendix 5. Of note, official guidance is also available from Merck Sharp & Dohme for management and drug discontinuation for certain irAEs in the pembrolizumab FDA label (Keytruda USPI). These irAEs include: pneumonitis, colitis, hepatitis, endocrinopathies (including hypophysitis, thyroid disorders, type 1 diabetes mellitus), and nephritis. This pembrolizumab-specific guidance is covered in the ASCO/NCCN guidelines; however, resources from Merck & Company for participants who develop these irAEs while on the pembrolizumab treatment arm are to be considered as well.

General management by NCI-CTCAE v5.0 grading, as per ASCO, is listed below:

- Grade 1: study treatment should be continued with close monitoring, with the exception of some neurologic, hematologic, and cardiac toxicities.
- Grade 2: study treatment may be suspended for most Grade 2 toxicities, with consideration of resuming when symptoms revert to Grade 1 or less. Corticosteroids may be administered (initial dose of 0.5 to 1 mg/kg/d of prednisone or equivalent).

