This appendix provides recommendations to the Investigators for the management of irAEs. The contents are based on the NCCN irAE management guidelines (in Accordance with the Joint American Society of Clinical Oncology Clinical Practice Guidelines and National Comprehensive Cancer Network, Brahmer JR, 2018) and FDA recommendations to require permanent treatment discontinuation for G4 irAEs (unless otherwise indicated in the tables below). Differences with ASCO/NCCN irAE management guidelines as recommended by the FDA are shown in bold and underlined text in the tables below. Critical instructions include the requirement that treatment must be permanently discontinued for the following Grade 4 irAE toxicities: Rash/inflammatory dermatitis, nephritis, autoimmune hemolytic anemia, hemolytic uremic syndrome, aplastic anemia, immune thrombocytopenia, acquired TTP, and in certain circumstances, lymphopenia.

Adapted from:

PPD

-Related Adverse Events in Patients Treated With Immune Checkpoint Inhibitor Therapy: American Society of Clinical Oncology Clinical Practice Guideline

Table of Tables

Table A1	Management of Skin irAEs in Patients Treated With ICPis.....	105
Table A2	Management of GI irAEs in Patients Treated With ICPis.....	110
Table A3	Management of Lung irAEs in Patients Treated With ICPis	114
Table A4	Management of Endocrine irAEs in Patients Treated With ICPis ...	115
Table A5	Management of Musculoskeletal irAEs in Patients Treated With ICPis	120
Table A6	Management of Renal irAEs in Patients Treated With ICPis.....	124
Table A7	Management of Nervous System irAEs in Patients Treated With ICPis	126
Table A8	Management of Hematologic irAEs in Patients Treated With ICPis	131
Table A9	Management of Cardiovascular irAEs in Patients Treated With ICPis	138
Table A10	Management of Ocular irAEs in Patients Treated With ICPis	140

Table A1 Management of Skin irAEs in Patients Treated With ICPis

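### For Grade 2 pneumonitis, the printed steroid start dose, weekly step and taper duration do not fit together over nearly all of their range, and only one of two readings stays within the 12-week steroid limit in Section 6.8.2

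*Protocol*

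**What the plan says.** Four places in the protocol bear on this.

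- **Appendix 5, Table A3, 3.1 Pneumonitis, Grade 2 row.** Study treatment is held until the event is Grade 1 or less, and the steroid instruction is "Prednisone 1-2 mg/kg/d and taper by 5-10 mg/wk over 4-6 weeks". It fixes a start dose, a weekly step and a duration, but no dose at which the taper ends.
- **Section 6.8.2, general guidance.** "Inability to reduce corticosteroid dose to 10 mg or less of prednisone or equivalent per day within 12 weeks is an indication" for permanent discontinuation of treatment, except where steroids are hormone substitution. The section does not say when the 12 weeks begin.
- **Section 6.9.2, general management by grade.** For Grade 2 immune-related events: "Corticosteroids may be administered (initial dose of 0.5 to 1 mg/kg/d of prednisone or equivalent". This overlaps the Table A3 range only at 1 mg/kg/d.
- **Section 4.3.** The highest Phase I dose, 30 mg/kg, is converted to "2100 mg for a 70-kg participant (the median body weight in the current dataset", and to 2400 mg at 80 kg, described as "corresponding to a typical median body weight for solid tumor type participants". These are the only two body weights the protocol offers for such a conversion.

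The additional considerations in Table A3 also provide for steroid courses longer than 12 weeks, in the context of prophylaxis.

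**The concern.** A start dose, a constant weekly step and a duration together determine the dose at the end of the taper. If that dose is still high when the stated duration is over, an investigator cannot follow both the step and the duration and has to choose one.

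The choice matters because Section 6.8.2 attaches a consequence to the speed of reduction. A site that keeps to the weekly step may still be above 10 mg/d at 12 weeks while following the table. A site that keeps to the 4-6 weeks will not be. The same event could therefore lead to quite different steroid courses and, in some cases, to a different decision about study treatment. Section 6.9.2 lists immune-related pneumonitis among the important identified risks of M7824. The SAP tabulates both TEAEs and immune-related AEs that lead to permanent discontinuation (15.1.2 and 15.2.3.2), so divergent readings could reach reported safety outputs.

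**Working it through.** **Inputs.** Start 1-2 mg/kg/d, step 5-10 mg/wk, duration 4-6 weeks (Table A3). Limit 10 mg/d by 12 weeks (Section 6.8.2). Weights 70 and 80 kg (Section 4.3). The weights check against the printed conversions: 30 × 70 = 2100 mg and 30 × 80 = 2400 mg.

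**Assumptions.** A constant weekly step, counted from the first reduction, with no time at full dose beforehand. Time at full dose would lengthen every figure. Weeks are rounded up.

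**Can the printed 4-6 weeks be reproduced?** At 70 kg the start is 70 × 1 = 70 to 70 × 2 = 140 mg/d. The amount removed is step × weeks: at least 5 × 4 = 20 mg and at most 10 × 6 = 60 mg. What is left runs from 70 − 60 = 10 to 140 − 20 = 120 mg/d.

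Weeks to a target = (start − target) / step. At 70 kg:

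| Start | Step (mg/wk) | Left at 4 wk | Left at 6 wk | Weeks to 0 | Weeks to ≤ 10 mg/d |
|---|---|---|---|---|---|
| 70 mg (1 mg/kg) | 10 | 30 | 10 | 7 | 6 |
| 70 mg (1 mg/kg) | 5 | 50 | 40 | 14 | 12 |
| 105 mg (1.5 mg/kg) | 10 | 65 | 45 | 11 | 10 |
| 105 mg (1.5 mg/kg) | 5 | 85 | 75 | 21 | 19 |
| 140 mg (2 mg/kg) | 10 | 100 | 80 | 14 | 13 |
| 140 mg (2 mg/kg) | 5 | 120 | 110 | 28 | 26 |

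The duration is not reproduced for an end dose of zero: the fastest combination takes 7 weeks. For an end dose of 10 mg/d it is reproduced at one point only (1 mg/kg, 10 mg/wk, 6 weeks).

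**How far the step and duration are apart.** Reaching zero in 4-6 weeks implies 70/6 = 11.7 to 70/4 = 17.5 mg/wk from 70 mg, and 140/6 = 23.3 to 140/4 = 35 mg/wk from 140 mg, against the printed 5-10. This measures the gap and is not a proposed step.

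**Dependence on weight.** To be at 10 mg/d by week 6, the start may be at most 10 + 6 × 10 = 70 mg at the faster step and 10 + 6 × 5 = 40 mg at the slower. At 2 mg/kg that means 35 kg or 20 kg. At 1 mg/kg it means 70 kg or 40 kg. Zero by week 6 needs a start of 60 mg or less, so 60 kg or less at 1 mg/kg and the faster step. The mismatch therefore covers most of the printed range at ordinary adult weights.

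**Against the 12-week limit, if the step governs.** The largest start that reaches 10 mg/d in 12 weeks is 10 + 12 × 10 = 130 mg at the faster step (130/70 = 1.86 mg/kg) and 10 + 12 × 5 = 70 mg at the slower (1.0 mg/kg). So at 70 kg, 2 mg/kg misses the limit at every printed step, and the slower step misses it for any start above 1 mg/kg. At 1 mg/kg both steps meet it, the slower one exactly. Spread evenly over dose and step, the share past 12 weeks is the average of (130 − 12 × step)/70 over steps of 5 to 10, which is (1 + 1/7)/2 = 57%. This describes the printed range and does not predict practice. At 80 kg, reaching 10 mg/d takes 7-14 weeks from 80 mg and 15-30 weeks from 160 mg.

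**If the duration governs,** the taper is over by week 6 and the limit is not approached.

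**With the Section 6.9.2 range.** At 70 kg, 0.5-1 mg/kg/d is 35-70 mg/d. At the Table A3 steps this reaches 10 mg/d in 3 weeks (25/10, rounded up) to 12 weeks (60/5), so it stays within the limit. Which Grade 2 range a reader takes changes the answer.

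**The case against.** A reader might infer that the instruction is arithmetically impossible. The documents do not support that. No end dose is printed, one combination at 70 kg arrives exactly at 10 mg/d (the threshold in Section 6.8.2), and a participant of 60 kg or less at 1 mg/kg and the faster step does reach zero in 6 weeks. The 70 kg figure is also a Phase I median, not a weight observed in this trial.

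A reader might also infer that following the table forces permanent discontinuation. That goes too far. The rule speaks of an inability to reduce, and a planned taper that is proceeding is not plainly that. It creates an indication, and the same section introduces its event-specific cross-references with "Permanent Treatment discontinuation may be recommended, so the relevant section must be reviewed". Appendix 5 describes itself in these terms: "This appendix provides recommendations to the Investigators for the management of irAEs". Section 7.1 allows one reinitiated course after discontinuation for an adverse event that has been managed or resolved, subject to agreement. The overrun also needs the step to prevail over the stated duration, and even then covers only part of the range.

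Nor does holding treatment until Grade 1 contradict the 12-week rule: one concerns the grade of the event, the other the steroid dose, and both can apply to the same participant.

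Finally, no effect on the comparison is shown. The rules apply to both arms, Section 6.9.2 describes the spectrum of immune-related events as similar, and the number of Grade 2 pneumonitis cases that would be affected is not known. SAP 6.6 records that the study was discontinued after the PFS interim analysis, which reduces the practical gain from an amendment.

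These objections limit the consequence. They do not remove the inconsistency: the text does not say whether step or duration prevails, and at the higher doses or the slower step that decides whether the 12-week limit is met.

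**Conclusion.** The point holds as an internal inconsistency in a safety instruction for an important identified risk. At 70 kg the step and duration together leave 10-120 mg/d, and they agree with an end dose of 10 mg/d at a single point of the printed range. If the step governs, the 12-week limit is missed at 2 mg/kg (13-26 weeks) and at the slower step for any start above 1 mg/kg. If the duration governs, it is not missed at all. The differing general Grade 2 range in Section 6.9.2 adds to the ambiguity.

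This rests on a constant weekly step, no time at full dose before the taper, and 70 kg as an illustrative weight. At 80 kg the times are longer. The conclusion is about wording that needs correction on patient-safety grounds. It is not a finding of bias between arms, and no primary-endpoint, alpha or sample-size figure changes.

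**What to change.** Reconcile the Grade 2 row of Table A3 (3.1 Pneumonitis), the 12-week rule in Section 6.8.2 and the general Grade 2 guidance in Section 6.9.2, so that start dose, weekly step, duration and end dose are consistent with one another and with the limit. In Section 6.8.2, state when the 12 weeks begin and whether a taper still on the tabulated schedule counts as an inability to reduce. Say which text prevails when the general guidance and the organ-specific table differ. The choice of values belongs to the sponsor's medical team, and none is suggested here.

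The cost is one table cell, one or two clarifying sentences in Section 6.8.2 and a cross-reference in Section 6.9.2. No analysis, sample-size calculation or data collection has to change.
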